Motivation, competence, and opportunity are important aspects to consider in relation to changing the behaviour of health care professionals¹². In interviews with POCUS users who were early adopters of the

technology, they reported that POCUS can increase their job satisfaction, professional contentment, and sense of performance¹³. It is not known if this also applies if POCUS is implemented broadly to GPs.

From a national survey⁸, we found that Danish GPs see the potential in using POCUS, but have concerns about capability (lack of guidelines and education in the use of POCUS) and opportunity (economical aspects, time pressure and workload). Furthermore, half of Danish GPs report at least one burnout symptom¹⁴. Hence, if POCUS is implemented on a larger scale in general practice, it will be important to evaluate how it affects the GP population.

Patients' perspectives and safety

Danish patients scanned in the GPs' office described that POCUS improved the service and quality in care¹⁵. However, there are no reported safety data regarding a broad implementation of POCUS in general practice and problems relating to the initial phase. Therefore, a surveillance of adverse events during the implementation could contribute with new knowledge about patient safety by identifying scanning types and procedures that potential carry a risk, when GPs begin using POCUS.

Health economics

Despite the fact that POCUS has been broadly implemented in primary care in some countries⁷ there are very few studies describing the cost-effectiveness of this⁵. In addition, transferring cost-effectiveness evaluations from one health care system to another can be challenging¹⁶. In a Danish health economic evaluation of women consulting their GP due to vaginal bleeding early in their pregnancy, we found that it was cost-effective to have the GP scanning compared to usual practice (referral to specialist in private gynaecology practices or hospital departments)¹⁷. However, there is a need for a broader health economic evaluation of implementing this technology in general practice.

Organizational aspects

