Hydronephrosis (kidney) ³¹	70.2	75.4	46%	95%
Viable intrauterine pregnancy (uterus) ³²	97.0	98.0	87%	93%
Joint effusion (knee) ³³	84.0	93.0	46%	73%
Gallstone (Gall bladder) ³⁴	89.8	88.0	64%	98%
Second teaching seminar				
Ascites (abdominal FAST) ³⁵	100.0	100.0	37%	85%
Intrauterine device location (uterus)**			86%	95%
Constipation (Rectum diameter)*** ³⁶	95.5	94.1	19%	46%
Subcutaneous abscess (skin) ³⁷	96.2	82.9	42%	98%
Pleural effusion (lung) ³⁸	88.0	90.0	28%	76%

*Diagnostic accuracy of POCUS reported in studies using the same scanning protocol as we intend to use in this intervention.

** No studies have been identified, where ultrasound is compared to a gold standard e.g. MRI or CT scan

*** Using POCUS for measuring rectal diameters as part of the ROM-IV criteria for diagnosing constipation in children is a relative new scanning modality and as such the GPs participating in the above-mentioned studies, have not been trained to perform the examination. However, the examination has been included in the NICE guidelines and the patient category is common in general practice.

Actioncards

A basis of the educational intervention are *actioncards* designed for each POCUS scanning modality (figure 4). The *actioncards* are 1-page instructions specifying the indication for performing the POCUS examinations, the transducer and specific equipment settings needed to perform the examination, the POCUS procedure including transducer placement, image acquisition and optimization, the interpretation of the examination, possible pitfalls to be aware off and integration of findings into a clinical context³⁹.

The *actioncards* are used as résumés of the preparation literature, to structure the examination during the teaching seminars and as supporting guidelines that can be used or consulted during the examination if needed.

[figure not shown]
Instruction videos

An instruction video is developed for each scanning modality included in the curriculum. All instruction videos are built with a structure similar to the structure of the *actioncards*: (1) Description of the indication for the examination, (2) Description of the needed equipment and equipment settings, and (3) demonstration of the conduction of the POCUS examination including tips and tricks regarding transducer placement, patient cooperation, image optimization etc.

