As these patient questionnaires cannot be linked to other study data, the patients will be asked to provide the following background information about themselves: age, gender, level of education, employment, location of practice (region in Denmark) and area examine with POCUS during the consultation (abdomen, heart, lung, musculoskeletal, gynaecological).

GP registration of possible adverse events: (outcome S7)

For the registration of possible adverse events, we will use a questionnaire giving the GPs the possibility to explain in free text using their own words to explain (1) what was scanned, (2) circumstances surrounding the scan, (3) what happened, and (4) reflections after the scan. This reporting of cases will be anonymous. Data will be collected from the educational intervention to the end of the study. We will report the aggregated total number of monthly registrations for each participating GP. The free text elaborations will not be reported, but passed on to the safety committee (see section 5d). The registration of adverse events for the study does not substitute the GP's registration of untoward incidents required by Danish law (<https://stps.dk/da/ansvar-og-retningslinjer/vejledning/rapporteringspligt/>).

Evaluation of the patient pathway and quality of selected POCUS examinations: (outcome S8)

After the study (July 2024), participating GPs will be instructed to make an evaluation of the patient pathway following selected POCUS examinations. A separate protocol will be developed for this part. The GPs will be asked to make a registration for each patient, who has been examined with a specific POCUS examination. Based on information found in the medical record the GP is asked to register the following information for each patient: (1) If the patient had subsequent imagining following the index consultation where POCUS was used by the GP, (2) if the patient was later re-examined for the same health complaint by the same GP, (3) if the patient was later re-examined for the same health complaint by another physician, (4) if the diagnosis at the index consultation was used was later confirmed or dismissed, (5) if the ultrasound findings in the index consultation was later confirmed or dismissed, (6) if there were any adverse events identified that were related to the POCUS examinations or the following course for the patient.

Background characteristics of participating GPs

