The researcher cleaning the data set and responsible for analyzing the primary outcome will have no knowledge of participants. He is a researcher with a physiotherapy background.

Data collection, management, and analysis

18a Data collection - Plans for assessment and collection of outcome, baseline, and other trial data

Data will be collected at different timepoints (see Figure 2).

Register data: Data regarding different POCUS examinations, number of referrals, number of consultations will be delivered by PLSP (outcomes P1-P2, S1 and S5). The data are registered prospectively by participating GPs in the medical records during from October 2023 to June 2024. We will receive these data retrospectively from PLSP, who will use an algorithm to collect monthly aggregated data for each participating GP. Due to availability of reimbursement codes in the medical record system, primary outcome P1 is collected in months 3-21, while primary outcome P2 and S1 is collected in months 1-21.

From PLSP, we will receive the following aggregated data on patients (age, gender) calculated based on patient ID in the medical records in the clinics (CPR numbers). These data are extracted and transferred to CAM AAU anonymously.

GP questionnaire: For the cross-sectional questionnaire exploring burnout, stress and job satisfaction before and after the educational intervention, an online questionnaire will be distributed by email to participants and a possible reminder will follow after two weeks. The questionnaire will be collected through SurveyXact (Rambøll, Aarhus, Denmark).

The questionnaire collecting background characteristics on participating GPs will be collected on the first teaching seminar using a QR code to an online questionnaire SurveyXact (Rambøll, Aarhus, Denmark).

At the teaching sessions, participating GPs will be taught how to report AE and SAE related or possibly related to the use of POCUS as well as near-miss cases. These events will be reported as anonymous cases to the study adverse event committee in an online questionnaire specifically designed for this purpose. The participants will have a link for an online questionnaire in SurveyXact (Rambøll, Aarhus Denmark) where they will register: (1) Type of POCUS, (2) indication for the examination, (3) description of the event, (4) participant's reflections after the events and (5) questions for the adverse events committee.

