The principal investigator (CAA) will monitor the data collection and contact the project steering committee in case of problems related to data collection or the validity of the collected data. The principal investigator (CAA) will also contact the steering committee in case of participant drop-out.

21b Description of any interim analyses and stopping guidelines, including who will have access to these interim results and make the final decision to terminate the trial

n/a

22 Harms

Ultrasound examinations are safe to perform on patients and radiation-free procedures⁴⁵.

Previous studies have found high diagnostic accuracies of POCUS examinations in the hands of generalists such as GPs⁴⁶. Still, introducing a diagnostic test may lead to an increased number of incidental findings and possible over-detection and overdiagnosis. A previous review of 564 medical records from patients examined with POCUS in Danish general practice did not reveal any adverse events related to POCUS use (unpublished data). However, patients generally put a lot of emphasis on diagnostic tests. Hence, the GPs are taught how to communicate the limits of their POCUS examination to patients to avoid false expectations and false reassurance.

The participating GPs will be obliged to report any Suspected Unexpected Serious Adverse Reactions (SUSARs), Serious Adverse Events (SAEs) and Adverse Events (AEs) related or possibly related to the use of POCUS to the adverse event committee. This reporting does not substitute the GP's registration of untoward incidents required by Danish law (<https://stps.dk/da/ansvar-og-retningslinjer/vejledning/rapporteringspligt/>).

23 Auditing

n/a

Ethics and dissemination

A minority of Danish GPs (12%) are already using POCUS in general practice. They have assembled their POCUS education individually and they are using POCUS very differently¹². This study aims to explore the effects of a tailored educational program for GP, framing specific evidence-based POCUS examinations to the general practice context. All scanning modalities included in the curriculum have previously been tested and evaluated in Danish general practice. Focused POCUS use in general practice has the potential to lead to faster and more precise diagnosis for patients seen in general practice.

24 Research ethics approval

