5.2 Secondary outcomes

Outcome S1:

The number of monthly consultations will be summarized for each participating GP from October 2022 to June 2024. In a stepped wedge analysis model, we will compare the number of consultations sent from primary care BEFORE the intervention to the number of referrals sent AFTER the intervention.

Outcome S2:

We will summarize each participating GPs' answer to stress-related items in the BEFORE and AFTER questionnaire, to calculate the Cohen's PSS sum score (PSS-score).

We will report the mean(SD) or median [IQR] PSS-sum score BEFORE and AFTER for all participating GPs. In addition we will report the frequency of GPs with a PSS sum score ≥ 18 BEFORE and AFTER indicating a high level of stress (2).

Outcome S3:

We will summarize each participating GPs' answer to Job satisfaction-related items in the BEFORE and AFTER questionnaire, to calculate the Warr-Cook-Wall Job satisfaction sum score (WCW-score).

We will report the mean (SD) or median [IQR] WCW-sum score extracted from the 9 sub-items as well as the score of the one overall item BEFORE and AFTER for all participating GPs. In addition, we will report the frequency of GPs with a WCW-sum score ≤ 3 BEFORE and AFTER indicating low job satisfaction (2).

Outcome S4:

We will summarize each participating GPs' answer to burnout-related items in the BEFORE and AFTER questionnaire, to calculate the sum score of the three dimensions in the Maslach Burnout inventory (emotional exhaustion (9 items), de-personalization (5 items), and personal accomplishment (8 items)) (2).

We will report the mean(SD) or median [IQR] sum score for each dimension BEFORE and AFTER for all participating GPs.

Outcome S7:

We will summarize the total number of adverse events reported by the participating GP during the study in relation to the type of ultrasound examination performed.

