6.1. Register-based data

From PLSP, we will receive monthly aggregated data extracted from the medical-record system in the participating GPs' clinics from October 2022 to June 2024.

Data will be delivered as monthly aggregated data in separate models:

Model 1: including all scanning-specific remuneration codes registered in the participating clinics by participating GPs and for each code the corresponding age and gender of the patient.

Model 2.1: including the total number of consultations performed in the participating GPs' clinics further specified on the type of consultation.

Model 2.2: including the total number of scanning-specific remuneration codes performed in the participating GPs' clinics further specified on the 11 different codes.

Model 2.3: including the total number of referrals sent from the participating GPs' clinics further specified on the type of referral.

Model 3.1: including the total number of consultations performed by the participating GPs further specified on the type of consultation.

Model 3.2: including the total number of scanning-specific remuneration codes performed by the participating GPs further specified on the 11 different codes.

Model 3.3: including the total number of referrals sent by the participating GPs further specified on the type of referral.

Model 4: including all scanning-specific remuneration codes registered in the participating clinics by participating GPs and for each code, the corresponding type of consultation and any referral sent on the same patient on the same date as the on the same date as the scanning-specific remuneration code was used.

From PLSP, we will also receive a time-trend estimation based on all clinics in Denmark. This estimation will show the general development in number of remuneration code and referrals from October 2022 to June 2024. This data will be used to estimate the underlying time effect which is a confounder for the analysis.

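### SAP outcome S7 gives a raw adverse-event total by scan type, with no event class and no link to the scan counts already held, so it shows scan volume as well as risk

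*SAP*

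**What the plan says.** SAP 5.2 defines the S7 analysis in one sentence: "We will summarize the total number of adverse events reported by the participating GP during the study in relation to the type of ultrasound examination". SAP 9 puts S7 among the outcomes that receive descriptive statistics. It allows a number with a percentage but does not say what the percentage would be of.

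The reason for collecting these reports is in Protocol 6, under patients' perspectives and safety. Surveillance could add knowledge by "identifying scanning types and procedures that potential carry a risk, when GPs begin using POCUS".

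Protocol 18a says GPs are "taught how to report AE and SAE related or possibly related to the use of POCUS as well as near-miss cases", all through one online questionnaire. The form is described twice. Protocol 12 lists what was scanned, the circumstances, what happened and reflections, all in free text. Protocol 18a lists type of scan, indication, description, reflections and questions to the committee. Neither list has a field for near miss, AE or SAE. The free text goes to the safety committee and is not reported. Protocol 5d and SAP 8 say the committee handles the reports. Neither says that it classes them for S7.

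Scan numbers are available. SAP 6.1 describes Model 3.2 as "including the total number of scanning-specific remuneration codes performed by the participating GPs further specified on the 11 different codes". Protocol 18a says "primary outcome P1 is collected in months 3-21", and Figure 2 places the first course in month 4.

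**The concern.** S7 is the only patient-harm outcome that SAP 1 lists for the primary article. Two features limit what a reader can take from it.

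First, the total can pool near misses with serious harm. The same number could describe ten harmless slips or ten serious events.

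Second, a count by scan type depends on exposure. A common and safe scan can produce more reports than a rare and riskier one. Someone using the article to decide which scan to teach differently, or to drop from the curriculum, could pick the wrong one.

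**Working it through.** The documents state no expected event rate, no target and no precision for S7, so there is no planned figure to reproduce. The check compares the texts and then illustrates the effect of exposure.

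**Step 1: can class be recovered?** The inputs are the two field lists in Protocol 12 and 18a. Protocol 22 names several classes of event that GPs must report, and Protocol 18a adds near misses. No listed field separates them. The description of what happened would let the committee do so, but no text says that this happens before counting. Mixing is therefore possible, not certain.

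**Step 2: is there a denominator?** S7 names none. Model 3.2 holds coded scans by code. Protocol 12 opens the S7 window at the educational intervention. Codes are collected from month 3 and the first course is in month 4, so the code data cover the whole S7 window.

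**Step 3: how much could exposure matter?** This step rests on assumptions. Table 1 gives the share of current users who perform each scan: 87% for viable pregnancy, 28% for pleural effusion and 19% for constipation. Assume that coded scans are proportional to these shares.

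- Ratio of volumes, pregnancy to constipation: 87/19 = 4.58.
- Without constipation, because the Table 1 footnote says "the GPs participating in the above-mentioned studies, have not been trained to perform the examination": 87/28 = 3.11.

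Now assume 20 scans per percentage point: 87 × 20 = 1,740 and 19 × 20 = 380. The rate per 1,000 is 1,000 × k/n. The exact Poisson limits for a count k are χ²(0.025; 2k)/2 and χ²(0.975; 2k+2)/2. The event counts are also assumed.

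| Assumed reports / scans | Per 1,000 scans | Exact 95% CI |
|---|---|---|
| 5 / 1,740 | 2.9 | 0.9 to 6.7 |
| 5 / 380 | 13.2 | 4.3 to 30.7 |
| 8 / 1,740 | 4.6 | 2.0 to 9.1 |
| 3 / 380 | 7.9 | 1.6 to 23.1 |

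- Equal counts (5 and 5): the rates differ 4.6-fold.
- Unequal counts (8 and 3): the count puts the first scan higher and the rate puts the second higher.
- Equal risk of 5 per 1,000: expected counts are 5 × 1.74 = 8.7 and 5 × 0.38 = 1.9, so the counts differ 4.6-fold with no difference in risk.

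With five times as many scans (8,700 and 1,900), 5 reports each give 0.57 and 2.6 per 1,000. The ratio is unchanged. In both comparisons in the table the intervals overlap, so counts this small would not settle which scan is riskier.

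**The case against.** The strongest reply is that S7 promises little. Protocol 7 and SAP 1 ask only for a description of reported events. The wish to identify risky scan types stands in the background section, worded as something surveillance could contribute. That is correct: the SAP does not undertake to rank scan types, and a count can still flag one. What remains is that the summary serves its own stated reason poorly when a better one can be made from data already held.

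Scan numbers may also be visible elsewhere. SAP 4 plans patients' age and gender by remuneration code, which would ordinarily show how many were scanned per code. A reader might infer that the trial lacks a denominator. It does not; S7 simply leaves it unused.

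S8 also records adverse events, for each reviewed patient. But it covers selected examinations only, is collected after the study, has its own protocol and is reported in a separate article.

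On class, near misses are named alongside AEs and SAEs, so a literal count of adverse events might leave them out. The questionnaire itself is not in the documents, and the field lists may be summaries. This supports saying that S7 can mix classes, and nothing stronger.

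With few events, many cells would be empty and rates unstable. That stands, and is why the intervals and the raw counts should be printed together.

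**Conclusion.** The point holds as a cheap improvement to a descriptive secondary outcome. No primary result is affected. S7 as written does not separate classes of event and does not relate reports to scans, so its counts reflect volume as well as risk. This conclusion needs only that scan types differ in volume.

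The 4.6-fold and 3.1-fold figures are illustrations. Table 1 gives the share of existing users who do a scan at all, not how often they do it, and the scan and event counts above are assumed.

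Two stronger readings are tempting. One is that S7 should be set beside the earlier record review in Protocol 22, which found no adverse events in 564 records. GP reports over billed scans are ascertained differently from a record review, so a rate from S7 would not be comparable either. The other is that S7 contradicts the anonymity of the reports, because Protocol 12 also says "We will report the aggregated total number of monthly registrations for each participating GP" and no listed field identifies the GP. If anonymity refers to the patient there is no conflict, and the SAP does not carry that output forward. It is a wording matter.

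**What to change.** In SAP 5.2, under S7:

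1. Before counting, the safety committee classes each report as near miss, AE or SAE and assigns it to one of the 11 codes.
2. Tabulate counts by class and scan type (3 × 11 = 33 cells).
3. Beside each scan type's total, show the coded scans from Model 3.2 over the S7 window and the reports per 1,000 coded scans, with an exact 95% confidence interval.
4. Describe the rate as GP-reported events over billed scans. Protocol 22 obliges GPs to report, but reporting may be incomplete. State how many GPs supplied codes.

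In Protocol 12, delete the monthly count per GP or say that anonymity refers to the patient.

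The cost is one grading pass, one table and a few sentences, with no new form field.

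The downside is that the denominator can be too small and the rate too high:

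- Scans in the course months may be uncoded, because Protocol 9 makes the fee claimable only after course attendance.
- Training scans, for example on family members (Protocol 11a), may be uncoded.
- Some clinics may send no individual data (SAP 9.2).

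Keep the counts beside the rates for this reason. Add a sensitivity rate limited to events and scans after course completion if event dates allow. Neither field list shows a date or identifies the GP. If only a submission date exists, a single calendar cut-off after the last cluster's third seminar would serve approximately.
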